2 STUDY OBJECTIVES AND ENDPOINTS

The objectives of this study are as follows:

Primary objective:

- To assess the objective response rate (complete and partial responses), following the administration of cabozantinib for 12 weeks in patients with locally advanced biopsy-proven non-metastatic ccRCC prior to undergoing surgery.

Secondary Objectives:

- To assess the safety, and tolerability of neoadjuvant cabozantinib.
- To determine the clinical outcome (DFS, OS) of patients with non-metastatic ccRCC who treated with neoadjuvant cabozantinib.
- To evaluate the surgery related outcomes.
- To evaluate correlative studies, including biomarkers, quality of life, and frailty/sarcopenia assessment of patients with non-metastatic ccRCC who are treated with neoadjuvant cabozantinib.

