3 STUDY DESIGN

Patients with renal cell carcinoma with clear cell component will be enrolled to receive neoadjuvant cabozantinib for 12 weeks before surgical resection. If patients are eligible and want to be part of the study, the patients will participate for up to 3 years.

Each subject's course will consist of four periods:

- A Pre-Treatment Period in which subjects are consented and undergo screening assessments to be qualified for the study (Section 5.1);
- A Treatment Period in which subjects receive study treatment and undergo study assessments. This period will end at the time of completion of cabozantinib, or when the patient withdraws consent or experiences unacceptable toxicity (Section 5.2);
- A Post-Treatment Period in which subjects no longer receive study treatment and undergo kidney surgery (Section 5.3). This period also includes intraoperative and post-operative period.
- A Long-Term Follow-up Period in which subjects will be follow after surgery (Section 5.4)

Study Treatment Discontinuation

Subjects may discontinue study treatment or withdraw their consent to participate in the study at any time without prejudice. The investigator may withdraw a subject from study treatment or from the study if, in his or her clinical judgment, it is in the best interest of the subject or if the subject cannot comply with the protocol.

In addition, any of the following conditions require discontinuation of the subject from study treatment:

- An AE or intercurrent illness that in the opinion of the investigator warrants the subject's withdrawal from study treatment;
- The investigator believes it is not in the best interest of the subject to continue on study
- Specific conditions described in the Management of Adverse Events Section 6.3.2;
- Necessity for treatment with other anticancer treatment prohibited by protocol;
- Sexually active subjects of childbearing potential who refuse to use medically accepted barrier methods of contraception (eg, male condom, female condom) during the course of the study and for 4 months after discontinuation of study treatment;
- Women who become pregnant or are breastfeeding;

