5.2 Treatment Period

During the Treatment Period subjects will receive cabozantinib for 12 weeks or until the occurrence of unacceptable drug-related toxicity or for other reason(s) for subject withdrawal as described in Section 3. Subjects should be instructed to immediately inform the investigator or study team member of any AEs.

The following schedule of assessments applies to all subjects (Table 5-1). More frequent assessments should be obtained if clinically indicated.

Table 5-1: On Study Assessments

	Study Treatment Period			Post-Treatment Period	Long-Term follow up Period
	Screening ^a	Week 1 Day 1 ^m	Week 2, 6 Day 1 (± 5 days)	Within 14 days after last dose	
Informed consent	X				
Demographics	X				
Medical and cancer history/demographics	X				
Physical examination	X	X	X	X	
Height	X				
Weight	X	X	X	X	
Vital signs	X	X	X	X	
ECOG performance status	X	X	X	X	
Clinical laboratory tests ^b	X	X	X	X	
Urinalysis and UPCR	X	X	X ^c	X	
PT/INR, PTT	X	X	X ^c		
TFTs (TSH, free T3, free T4)	X		X ^c	X	
12-lead ECG	X	X	X ^c	X	
ECHO or MUGA ^j	X				
Cabozantinib administration		X (daily)	X (daily)		
Urine Pregnancy test ^l	X	X	X ^c	X	
Tumor assessment ^d	X		X ^c	X ⁿ	X ^e
Concomitant medications		X	X	X	
Adverse events		Continuous		X	
Follow-up				X	X ^f
Blood for correlative studies		X	X ^c	X	X ^k
Pathologic Confirmation of clear cell component	X				
Quality of life questionnaires ^h		X	X ^c	X	
Frailty assessment ^l		X	X ^c	X	
Sarcopenia assessment		X	X ^c	X	
Kidney Surgery				X ^g	

ECG, electrocardiogram; ECOG, Eastern Cooperative Oncology Group; PT/INR, prothrombin time/International Normalized Ratio; PTT, partial prothrombin time, TFT, thyroid function test; UPCR, urine protein/creatinine ratio

^a Screening will be done within 28 days before the 1st dose.

^b laboratory tests should include a standard hematology panel (CBC, differential, platelets) and chemistry panel (albumin, alkaline phosphatase, ALT, amylase, AST, bicarbonate, bilirubin, blood urea nitrogen, calcium, chloride, creatinine, γ -glutamyltransferase [GGT], glucose, lactate dehydrogenase, lipase, magnesium, phosphorus, potassium, sodium, total protein). CRP

^c Week 6 only

^d All sites of known disease must be assessed.

^e Surveillance scan after surgery will be obtained per investigator.

^fPatients in long term follow-up can be seen by medical oncology or urology team, have chart reviewed, or phone call to determine current status every 3 months. (+/- 14 days).

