5.4 Long Term Follow-up Period

After kidney surgery, patients will enter the long term follow-up period. Data to determine a patient's current status may be collected from clinic visits with either medical oncology or urology ,chart review, or phone call every 3 months (+/- 14 days) until disease recurrence, initiation of new antineoplastic or investigational therapy, whichever occurs first. During this period, surveillance imaging will be obtained per investigator. A final blood sample for correlative studies will be collected after surgery. Patients removed from study for unacceptable adverse event(s) will be followed until resolution or stabilization of the adverse event.

Long-term follow-up continues until the patient's withdrawal of consent or loss to follow up, death, or study termination.

A participant will be considered lost to follow-up if he fails to return for three scheduled visits and is unable to be contacted by the study site staff after three attempts at contact by phone.

The following actions must be taken if a participant fails to return to the clinic for a required study visit:

- The site will attempt to contact the participant and reschedule the missed visit and counsel the participant on the importance of maintaining the assigned visit schedule and ascertain if the participant wishes to and/or should continue in the study.
- Before a participant is deemed lost to follow-up, the investigator or designee will make every effort to regain contact with the participant (where possible, 3 telephone calls and, if necessary, a certified letter to the participant's last known mailing address or local equivalent methods). These contact attempts should be documented in the participant's medical record or study file.
- Should the participant continue to be unreachable, patient will be considered to have withdrawn from the study with a primary reason of lost to follow-up.

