9 STATISTICAL CONSIDERATIONS

The primary outcome is objective response rate (complete and partial responses) at week 12 after the administration of cabozantinib. The Simon's two-stage design will be adopted for a possible early termination for futility. We hypothesize that there is > 24% response rate at 12-week and a rate < 5% will be considered as futility. In the first stage, 11 patients will be accrued (this does not include screen failures), and if there is no responses among them, the study will be stopped for futility. Otherwise, additional 6 patients will be accrued for a total of 17 patients. The null hypothesis will be rejected if there are 3 or more responses in 17 patients. The design yields a type I error rate of 0.05 and power of 80% when the true response rate is 24%. The final response rate will be estimated with 95% confidence interval by binomial test.

The safety profile of the treatment will be documented and summarized by summary statistics as frequency and percentage for each AE. We will do safety assesment after the first 6 patients without pausing the enrollment.

For disease free survival (DFS), which was defined as the interval between time of surgery and the first tumor recurrence, or death. Patients will be censored at time of last follow-up. For overall survival, death from any cause will be defined as the event. Patients will be censored at time of last follow-up. Overall survival (OS) and disease free survival (PFS) will be estimated

with the Kaplan-Meier method. The DFS and OS of each patient group at specific time points, such as 6 months, 1 year, and 3 year, etc. will be also estimated along with 95% CI.

For the biomarker study, descriptive statistics will be first used to summarize biomarker endpoints, including analyses of tumor biopsies. Biomarker data will also be displayed graphically, where appropriate. Depending on whether data is normally distributed, t-test or Wilcoxon rank sum test will be used to compare each biomarker between any two groups stratified by response or other factors, respectively. Logistics regression model will be further employed to test the adjusted effect of biomarker on the response rate after adjusting for other factors.

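### DFS is censored at last follow-up, which may be a phone call or chart review, so it is open to upward bias whenever contact outlasts the last disease assessment

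*Combined protocol and SAP*

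**What the plan says.** Section 2 makes DFS a secondary objective: "To determine the clinical outcome (DFS, OS) of patients with non-metastatic ccRCC". Section 9 defines it as the time from surgery to "the first tumor recurrence, or death. Patients will be censored at time of last follow-up". OS gets the same censoring rule. Both are to be estimated by Kaplan-Meier: "The DFS and OS of each patient group at specific time points, such as 6 months, 1 year, and 3 year, etc", with 95% intervals.

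The follow-up that sets the censoring date is described in two places. Section 5.4 lets status come from a clinic visit or "chart review, or phone call every 3 months (+/- 14 days) until disease recurrence, initiation of new antineoplastic or investigational therapy". Footnote f of Table 5-1 (Section 5.2) likewise lets patients be seen in clinic, "have chart reviewed, or phone call to determine current status every 3 months". On imaging, Section 5.4 says "During this period, surveillance imaging will be obtained per investigator", and footnote e of Table 5-1 says "Surveillance scan after surgery will be obtained per investigator". Neither gives an interval.

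Section 5.6 schedules scans only at baseline, week 6 and week 12. No section says how a post-surgical recurrence is established, requires an assessment before a patient counts as recurrence-free, or ties DFS censoring to an assessment.

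**The concern.** A phone call settles whether a patient is alive, so last-contact censoring suits OS. It cannot exclude an asymptomatic recurrence. Take a patient whose last clear scan is at month 6 and who is phoned every 3 months until month 30. Under Section 9 this patient is censored disease-free at month 30, although an asymptomatic recurrence after month 6 had no route into the data. Such patients stay in the Kaplan-Meier risk set and hold the curve up, more so at later landmarks.

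The trial has one arm, so no control group shares the same ascertainment, and landmark DFS would be taken at face value. With 17 patients, 20% unscanned is only 3 or 4 people (0.20 × 17 = 3.4). Section 15.4 also says that standard-of-care assessments may not need CRF entry. If surveillance scans fall under that, the problem could be neither measured nor repaired later.

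**Working it through.** The plan states no DFS figure to reproduce. Its only computed figures belong to the two-stage response-rate design, which this point does not touch.

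**Inputs from the documents.** Contact every 3 months by visit, chart review or call; imaging interval not stated; censoring at last follow-up.

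**Assumptions, because the documents are silent.** Exponential recurrence with true 1-year DFS S₁ of 75% or 65%. Scans every 6 months. A fraction f of 20% or 40% with no scan after month 6. Contact to month 30 for everyone. Unscanned recurrences either never surface, or surface as symptoms after an exponential lag with mean L of 6 or 12 months. Deaths without recurrence are ignored.

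**Rule as written, at 2 years.** Nobody is censored before month 30, so the Kaplan-Meier value is a mixture:

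DFS(24) = (1 − f)·S₁² + f·S₁^0.5·Q

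Q is the chance that an unscanned patient, clear at month 6, has no detected recurrence by month 24. If nothing surfaces, Q = 1. Otherwise, with h = −ln(S₁)/12, m = 1/L and w = 18 months:

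Q = (m·e^(−hw) − h·e^(−mw)) / (m − h)

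Example with S₁ = 0.75, f = 0.40:
- No symptoms: 0.6 × 0.5625 + 0.4 × 0.8660 = 0.684.
- L = 12: h = 0.02397, m = 0.08333, e^(−hw) = 0.6495, e^(−mw) = 0.2231, so Q = 0.822. DFS = 0.3375 + 0.4 × 0.8660 × 0.822 = 0.622.

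| True 1-year | Unscanned | True 2-year | Rule, lag 6 mo | Rule, lag 12 mo | Rule, no symptoms |
|---|---|---|---|---|---|
| 75% | 20% | 56.25% | 58.0% | 59.2% | 62.3% |
| 75% | 40% | 56.25% | 59.7% | 62.2% | 68.4% |
| 65% | 20% | 42.25% | 44.3% | 45.9% | 49.9% |
| 65% | 40% | 42.25% | 46.4% | 49.6% | 57.6% |

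The excess is 1.7 to 7.3 points with symptomatic detection, and 6.1 to 15.3 without (16 if rounded percentages are subtracted, 58 − 42).

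**At 1 year.** The same formula, with S₁ in place of S₁² and w = 6, gives 76–79% against 75% and 67–70% against 65% with symptoms. Without symptoms it gives 77–80% and 68–71%.

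**Censoring at the last scan instead.** Simulation of 1,000,000 patients per scenario, counting symptomatic recurrences as events:
- No symptoms: 56% against 56% and 42% against 42% at 2 years, so the bias is removed.
- Symptoms at a mean lag of 6–12 months: 50–54% against 56%, and 37–41% against 42%, so it undershoots.
- At 1 year with symptoms: 75% against 75%, and 65–66% against 65%.

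**Scanning continued to last contact.** In a separate simulation with median DFS of 18 or 36 months and everyone scanned every 3 or 6 months to last contact, last-contact censoring gave 3-year DFS of 0.25 against 0.25 and 0.50 against 0.50.

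**The case against.** A reader might infer that patients will go unscanned and that DFS therefore is biased upward. The documents do not say this. Table 5-1 marks tumor assessment in the long-term follow-up column, Section 5.4 says surveillance imaging will be obtained, and a chart review can retrieve a scan result. What is left open is the timing, so the text supports exposure to bias and not its presence. This part of the objection stands.

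The no-symptoms figures also need every unscanned recurrence to stay hidden despite status checks every 3 months. They are an upper case and should not be the headline. That stands too.

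A further tempting reading is that censoring at the last scan cures the problem. It does so only if no recurrence surfaces between scans. Otherwise symptomatic recurrences after the last scan count as events, while event-free patients leave the risk set at that scan. The estimate then falls below the truth. In the 75%, 40%, 6-month-lag case the last-scan error (50% against 56%) exceeds that of the current rule (60%).

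Finally, the endpoint is secondary, descriptive and imprecise: with 17 patients and DFS of 56%, a simple 95% half-width is 1.96 × √(0.56 × 0.44 / 17) = 0.24. That limits the weight of the point. It does not justify a rule that can credit unassessed time as disease-free, because a confidence interval does not show that kind of error.

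**Conclusion.** The point holds as a gap in the censoring rule. Section 9 gives DFS a censoring date that suits OS, and nothing elsewhere links it to a disease assessment. The direction of any error from lapsed scanning is upward. Its size depends on scan frequency, the share of patients who stop being scanned and how often recurrences surface as symptoms, none of which the documents give.

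Under the stated assumptions it ranges from near zero (regular scans to last contact), through about 2–7 points at 2 years (20–40% unscanned after month 6, symptoms at a mean lag of 6–12 months), to about 6–15 points if no unscanned recurrence surfaces.

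Two years is an illustrative landmark: Section 9 names 6 months, 1 year and 3 years as examples. Section 3 says "the patients will participate for up to 3 years". If that span includes the 12 treatment weeks and the minimum 28-day washout, 36 − 3.7 leaves about 32 months after surgery, so a 3-year figure may not be observable.

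A reader should not extend the point to response rate, the stopping rule or OS, which are unaffected. It should be corrected, but it does not threaten the trial's main conclusion.

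**What to change.** In Section 9, censor DFS for patients without recurrence or death at the last adequate disease assessment showing no recurrence, or at surgery if there was none. Define adequate assessment as imaging (including scans found by chart review) or a documented clinic disease evaluation; a call alone does not qualify. Keep last-contact censoring for OS.

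Report DFS censored at last contact as a sensitivity analysis. In the 2-year scenarios with symptoms, the truth lay between the two estimates. At 1 year the last-scan estimate was within about 1 point of the truth, sometimes slightly above it, so the pair is a guide and not a guaranteed bound.

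Record the date and result of every surveillance scan on the CRF, and report how many patients had an assessment by each DFS landmark.

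The cost is a few sentences in Section 9, CRF fields for each scan and one extra analysis, with no added scans. The downside is shorter DFS follow-up, wider late intervals and possible downward bias when symptomatic recurrences after the last assessment count as events, which is why both analyses should be shown.

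### Survival contact is scheduled only after kidney surgery and may stop at recurrence or new therapy, while OS has no stated origin or analysis set, so later deaths could be missed

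*Combined protocol and SAP*

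**What the plan says.** Section 2 lists DFS and OS in patients given neoadjuvant cabozantinib as a secondary objective, without limiting it to those who reach surgery. Section 4.1 admits tumours that the surgeon regards as unresectable.

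Section 9 starts DFS at surgery. For OS it says only: "For overall survival, death from any cause will be defined as the event. Patients will be censored at time of last follow-up". Both endpoints are to be estimated by Kaplan-Meier, with 95% intervals at times such as 6 months, 1 year and 3 years.

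On follow-up, Section 5.4 states: "After kidney surgery, patients will enter the long term follow-up period". Footnote f of Table 5-1 (Section 5.2) applies the 3-monthly contact to patients who are "in long term follow-up can be seen by medical oncology or urology team, have chart reviewed, or phone call to determine current status". Section 5.4 then gives two different end points. Status data are collected "until disease recurrence, initiation of new antineoplastic or investigational therapy, whichever occurs first", yet a later sentence continues long-term follow-up to the patient's "withdrawal of consent or loss to follow up, death, or study termination".

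For patients taken off for toxicity, Section 5.4 says: "Patients removed from study for unacceptable adverse event(s) will be followed until resolution or stabilization of the adverse event". It does not mention their survival status.

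**The concern.** Three things combine.

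- **OS is incompletely specified.** Without an origin and an analysis set, the analyst can start the clock at first dose or at surgery, and the two give different estimates in different patients.
- **Never-operated patients have no scheduled survival contact.** The 3-monthly check sits in a period that opens after surgery. Patients who progress, stop for toxicity or remain unresectable may never enter it.
- **Operated patients may be dropped at recurrence or new therapy.** A site that follows the first end point in Section 5.4 stops asking at that moment.

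Because OS is censored at last follow-up, patients lost in these ways leave the risk set at their last contact. Non-resection and recurrence are both linked to the disease, so this censoring is likely to be informative and OS can be overstated. Survival status that was not collected at the time may be hard to recover later.

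**Working it through.** The plan states no OS rate, event count or precision, so there is no OS figure to reproduce. Its only design figures are for response rate. An exact two-stage binomial calculation, summing P(X1 = x) × P(X2 ≥ 3 − x) over x ≥ 1 with 11 then 6 patients, gives type I error 0.0490 and power 0.8048, against the stated 0.05 and 80%. Nothing below changes those.

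**1. Last scheduled contact without surgery.** Inputs: 12 weeks of treatment (Section 6.2); a visit within 14 days of last dose (Section 5.3); a scan within 28 days (Table 5-1, footnote n); AE monitoring to 30 days after last dose, which is the only text that dates a last follow-up visit (Section 6.3.2). Take first dose as Day 1, no interruption, and 6 months as Day 183.

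- Full course: last dose is Day 84. Visit by 84 + 14 = Day 98; scan by 84 + 28 = Day 112; AE window to 84 + 30 = Day 114.
- Gap to the 6-month landmark: 183 − 114 = 69 days.
- Stopping for progression at the week 6 scan: Week 6 Day 1 is 5 × 7 + 1 = Day 36 (31 to 41 with the ±5 day window). Contact ends at 36 + 30 = Day 66 (61 to 71). Gap: 183 − 66 = 117 days (112 to 122).

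**2. What is still captured.** Section 8.1.4 covers all SAEs, hence all deaths, to 30 days after the decision to stop treatment. After that it covers only SAEs related to treatment or study procedures. Section 8.2.4 follows related SAEs and related AEs that led to discontinuation. Section 5.4 follows patients removed for toxicity until the event resolves or stabilises. The exposure is therefore to later deaths judged unrelated.

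**3. Effect of the missing origin.** Surgery comes at least 28 days after last dose (Section 5.3), so after a full course it falls no earlier than 84 + 28 = Day 112. A 6-month OS landmark then means Day 183 if counted from first dose, or 112 + 183 = Day 295 at the earliest if counted from surgery. An origin at surgery also removes never-operated patients from OS altogether.

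**4. Weight of one patient.** With 17 patients each is 1/17 = 5.9%. The documents give no death count, so assume d = 1, 2 or 3 true deaths by a landmark and no other censoring. One death is missed because that patient was censored earlier. The reported figure depends on whether that censoring falls before or after the counted deaths.

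| True deaths | True OS | Reported OS | Difference (points) |
|---|---|---|---|
| 1 | 16/17 = 94.1% | 100% | +5.9 |
| 2 | 15/17 = 88.2% | 15/16 to 16/17 = 93.8 to 94.1% | +5.5 to +5.9 |
| 3 | 14/17 = 82.4% | 14/16 to 15/17 = 87.5 to 88.2% | +5.1 to +5.9 |

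If a survivor, rather than a patient who dies, is censored before the d counted deaths, the change is (16 − d)/16 − (17 − d)/17 = −0.4, −0.7 and −1.1 points for d = 1, 2, 3.

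**The case against.** **The population is named.** Section 2 ties OS to treated patients. That is fair for the objective, but Section 9 does not carry it into an analysis set, and the origin is missing throughout.

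**Every subject is meant to be followed.** Section 3 says that each subject's "course will consist of four periods", with participation up to 3 years. Table 5-1 marks follow-up in the post-treatment column, and chart review is allowed. No text says that contact ends for a patient without surgery. This stands as a limit: the documents are silent on that patient, and early censoring is an inference from the schedule. But the fourth period is itself described as following surgery, and none of these texts schedules survival contact without it.

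**Section 5.4 also says until death.** Footnote f gives no stopping event, and the other sentence may end only the fixed 3-monthly collection. If the until-death sentence governs, the problem for operated patients disappears. The text does not say which governs, and the other two gaps remain.

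**Frequency is unknown.** Surgery is planned for everyone, and making unresectable tumours resectable is one of the potential advantages of neoadjuvant therapy listed in Section 1. The neoadjuvant axitinib series cited there saw no progression in its 24 patients. This stands, although that was a different drug.

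**The day counts are approximate.** They assume no interruption, treat the week 6 scan day as the last dose, and measure from first dose. Section 8 counts its 30 days from the decision to stop, not from last dose. The trial could also end at 11 patients. These points move the figures but do not supply the missing contact.

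**Conclusion.** The concern holds. Section 9 gives OS neither an origin nor an analysis set, the schedule provides no survival contact for a treated patient who never has surgery, and Section 5.4 contradicts itself on when status collection ends for those who do.

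The bias itself cannot be sized, because the documents give neither a non-operation rate nor a survival rate. On the stated assumptions a missed death moves OS up by about 5 to 6 points, and a survivor censored early moves it down by about 1 point or less. The direction therefore depends on who is lost; since non-resection and recurrence are linked to the disease, overstatement is the likelier result. OS is secondary and descriptive, so this should be corrected but does not threaten the primary analysis. Starting DFS at surgery is a legitimate definition and is not in dispute.

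**What to change.** 1. In Sections 3 and 5.4, give every treated patient, operated on or not, the same 3-monthly clinic, chart or phone status contact. Reconcile the two end points in Section 5.4 so that survival status is collected until death, withdrawal, loss to follow-up or study end, including after recurrence or new therapy. Align Table 5-1 and its footnote f.
2. In Section 9, define OS from first dose in all treated patients.
3. Keep DFS from surgery, state that it is restricted to operated patients and give its n. Report how many were not operated on, with reasons.

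The cost is wording in Sections 3, 5.4 and 9 and a matching edit to Table 5-1, plus a few extra contacts of a kind that Section 5.4 already allows. Reported OS may be less favourable. The response-rate endpoint, N = 17 and the Simon rule do not change. The change should be made while patients can still be contacted.

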5.6 Tumor Assessment

5.5.1 Efficacy Assessments

Objective response rate (ORR) is the primary endpoint for this study which will be evaluated using RECIST 1.1 criteria (14). Evaluation of response will follow the Response Evaluation Criteria in Solid Tumors (RECIST 1.1). All tumor measurements must be recorded in centimeters.

For the purposes of this study, patients should be re-evaluated for response at 12 weeks. This will be obtained after last dose of cabozantinib before surgical resection while waiting 28 days wash-out period. In addition to week 12 scan, week 6 scan should also be obtained to rule out rapid progression. Only scans at week 12 (prior to surgery) will be used for purposes of the primary objective. In order to have better response assessment, we will use same type of scan at baseline and at 12 weeks. Since patients are required to be non-metastatic disease patients, likely only target lesion assessment will be needed.

- **Target Lesions:**

All measurable lesions up to a maximum of two lesions per organ and 5 lesions in total, representative of all involved organs, should be identified as target lesions and recorded and measured at baseline. Lymph nodes must be at least 15mm in short axis to be included as a target lesion. Target lesions should be selected on the basis of their size (those with the longest diameter) and their suitability for accurate repeated measurements (either by imaging techniques or clinically). A sum of the longest diameter for all target lesions will be calculated and reported as the baseline sum longest diameter. The baseline sum of longest diameters will be used as the reference by which the objective tumor response is characterized.

- **Non-target Lesions:**

All other lesions (or sites of disease) should also be recorded at baseline. Measurements of these lesions are not required, but the presence or absence of each should be noted throughout follow-up.

5.5.2 Evaluation of Target Lesions:

- **Complete Response (CR):**

The disappearance of all target lesions.

- **Partial Response (PR):**

At least a 30% decrease in the sum of the longest diameter of target lesions, taking as reference the baseline sum longest diameter.

- **Progressive Disease:**

At least a 20% increase in the sum of the longest diameter of target lesions, taking as reference the smallest sum longest diameter recorded since the treatment started or the appearance of one or more new lesions.

- Stable Disease:

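### Section 9 relates biomarkers to tumour effect only through yes/no response; adding a prespecified analysis of percent change in tumour size is a cheap improvement

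*Combined protocol and SAP*

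**What the plan says.** Section 9 plans descriptive statistics and graphs for the biomarkers and names two inferential analyses. In the first, a "t-test or Wilcoxon rank sum test will be used to compare each biomarker between any two groups stratified by response or other factors"; the other factors are not defined. In the second, "Logistics regression model will be further employed to test the adjusted effect of biomarker on the response rate after adjusting for other factors". No alpha, effect size, power or multiplicity rule is given for the biomarkers.

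Response means complete or partial response. Section 5.6 (under 5.5.2) defines partial response as "At least a 30% decrease in the sum of the longest diameter of target lesions, taking as reference the baseline sum longest diameter". The same section has the baseline sum recorded and a week 12 scan of the same type as at baseline.

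Section 2 lists biomarkers within a secondary objective. Section 12.4 (Correlative studies) plans baseline tissue from all 17 patients. It says that functional results from blood cells may be checked for correlation with clinical outcome measures, but names neither the measure nor the method.

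**The concern.** Classifying a scanned patient against the 30% line requires both sums of diameters, so percent change can be derived without new data. Once the value is reduced to yes or no, a patient at −29% counts the same as one at +15%, and one at −31% the same as one at −80%. At the design rate this leaves a comparison of about 4 patients with 13, and an adjusted logistic model resting on about 4 events. A biomarker that tracks the amount of shrinkage could be missed. If percent change is analysed only after the results are known, the analysis will be post hoc and carry less weight.

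**Working it through.** **Inputs from the documents.** Stage 1 has 11 patients and stops at 0 responses; otherwise the trial continues to 17. The rule is that "The null hypothesis will be rejected if there are 3 or more responses in 17 patients". The response rates are 5% (null) and 24% (alternative). Section 1 cites neoadjuvant precedents of 19% (sunitinib) and 11/24 = 46% (axitinib).

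**Assumed, because the documents are silent.** Two-sided 5% per biomarker, no multiplicity adjustment, and a range of biomarker–shrinkage correlations.

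**1. The plan's own figures.** P(reject) = Σ over x = 1 to 11 of P(Bin(11,p) = x) × P(Bin(6,p) ≥ 3 − x). This gives 0.0490 at p = 5% and 0.805 at p = 24%. The stated 0.05 and 80% reproduce.

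**2. Number of responders.** 17 × 0.24 = 4.1. The precedents give 17 × 0.19 = 3.2 and 17 × 11/24 = 7.8, so about 3 to 8 is a plausible range.

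**3. Power under a graded relation.** Simulation with 40,000 trials per setting and n = 17: biomarker X standard normal, shrinkage Y = ρX + √(1 − ρ²)·E with E standard normal, and the k patients with the largest Y taken as responders. The exact Wilcoxon test of X between the k responders and the rest is compared with the Spearman correlation of X and Y.

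| ρ | 4 responders: Wilcoxon | 4 responders: Spearman | Loss (points) | 8 responders: Wilcoxon | 8 responders: Spearman | Loss (points) |
|---|---|---|---|---|---|---|
| 0.3 | 11% | 20% | 9 | 14% | 20% | 6 |
| 0.4 | 17% | 32–34% | 15–17 | 22% | 32% | 11 |
| 0.5 | 26% | 49–50% | 24 | 33% | 50% | 17 |
| 0.6 | 37–38% | 69% | 31 | 47% | 69% | 21 |

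Ranges show the spread between repeated simulations; losses were taken before rounding. The type I error of Spearman was 5.0% to 5.3%. The t-test against Pearson correlation gives a similar picture: with 4 responders at ρ = 0.5, 29% against 56%. At ρ = 0.2 the loss with 4 responders is only about 4 points.

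**4. Power if the biomarker differs only across the 30% line.** Here X is shifted by 1.5 SD in responders, with no gradient within either group. With 4 responders the Wilcoxon test has about 63% power and Spearman about 33%. The ranking reverses.

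**5. Too few responders for the planned test.** With one responder among 17, the smallest exact two-sided Wilcoxon p is 2/17 = 0.118. With none there is nothing to compare. Under the two-stage rule at 24%:
- 0 of 11, so the trial stops: 0.76^11 = 0.049
- exactly 1 of 17, which requires 1 of 11 and then 0 of 6: 11 × 0.24 × 0.76^10 × 0.76^6 = 0.033
- total: 0.049 + 0.033 = 0.082, about 8%

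Percent change could still be analysed in either case, in the patients with both scans.

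**The case against.** Objective response is the primary endpoint, so asking whether a biomarker relates to it is coherent and easy to interpret. Section 9 also allows grouping by other factors, puts description and graphs first, and may not be a closed list given Section 12.4. All of this stands as a reason to keep the responder comparison. It does not supply an analysis of percent change, because neither section names one.

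A reader might infer that the split costs a fixed 20 to 30 points of power. The documents do not support that. The loss depends on a correlation they do not give, and it runs from about 4 points at ρ = 0.2 to about 31 at ρ = 0.6 with 4 responders.

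A reader might also infer that the split has no benefit. That fails too: for a biomarker that changes only at the 30% line the planned test is clearly better, and nothing in the documents says which shape to expect.

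Finally, a plain binomial for 0 or 1 responder among 17 gives 6.0% at 24%. That ignores the stage 1 stop, and the figure for this design is about 8%.

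The practical gain is limited. Section 12.4 lists about ten tissue markers plus blood measures. If ten tests were Bonferroni-adjusted (an assumption), Spearman power would be about 19% at ρ = 0.5 and 34% at ρ = 0.6. Either analysis is hypothesis-generating.

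**Conclusion.** The point holds as a cheap improvement, not as an error in the plan. Section 9 uses only binary response for tumour effect, while a more informative measure is already available and unused. Under a graded, monotone relation at n = 17 and two-sided 5%, adding percent change recovers about 9 to 31 points of power with 4 responders, and about 6 to 21 with 8, for correlations of 0.3 to 0.6. These sizes rest on the assumed correlation and on normally distributed data. Under a pure threshold relation the advantage lies with the planned comparison, so the two analyses complement each other. The primary endpoint and its decision rule are unaffected.

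**What to change.** In Section 9, prespecify the Spearman correlation of each biomarker with percent change in the sum of diameters from baseline to the week 12 scan, in patients with both scans. Where adjustment is wanted, name a linear or rank regression on percent change. Keep the responder/non-responder comparison and report the two side by side.

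This takes about two sentences and needs no new patients, scans or samples. It has two costs. Patients without a week 12 scan leave the percent-change analysis, so their number should be reported. It also adds one more analysis per biomarker to results that have no multiplicity control, so Section 9 should call them exploratory.
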